#### ***13.2. Monitoring for Adverse Events***

At each visit, after the subject has had the opportunity to spontaneously mention any problems, the Investigator should inquire about AEs by asking if the patient has any problems.

#### ***13.3. Procedures for Recording and Reporting AEs and SAEs***

Subsequent to signing an informed consent form, all untoward medical occurrences that occur during the course of the study must be documented on an Adverse Event Form (AEF). A separate AEF must be filled out for each event. When possible, signs and symptoms indicating a common underlying pathology should be documented as one comprehensive event. For each recorded event, the AE documentation must include the onset date, outcome, resolution date (if event is resolved), intensity (i.e., severity), any action with study treatment taken as a result of the event, and an assessment of the adverse event's relationship to the study treatment.

#### **Nonserious Adverse Events**

A nonserious AE is defined as any untoward change in a subject's medical health that does not meet serious criteria noted below (e.g., is not life-threatening, does not require hospitalization, does not prolong a current hospitalization, is not disabling, etc.). All adverse events must be reported regardless of whether or not they are related to the study treatment.

For nonserious adverse events, an AEF containing all available information will be collected on a routine basis and submitted to the Medical Monitor at the close of the study.

### **Serious Adverse Events**

A serious adverse event (SAE) is defined as any adverse experience that meets any of the following criteria:

- Results in death.
- Is life-threatening.

NOTE: Life-threatening means that the subject was at immediate risk of death from the reaction as it occurred; i.e., it does not include a reaction which hypothetically might have caused death had it occurred in a more severe form.

- Requires inpatient hospitalization or prolongation of existing hospitalization.

NOTE: In general, hospitalization signifies that the individual remained at the hospital or emergency ward for observation and/or treatment (usually involving an overnight stay) that would not have been appropriate in the physician's office or an out-patient setting. Complications that occur during hospitalization are AEs. If a complication prolongs hospitalization or fulfills any other serious criteria, the event is serious. When in doubt as to whether "hospitalization" occurred, the event should be considered serious.

- Results in persistent or significant disability/incapacity. Disability is defined as a substantial disruption of a person's ability to conduct normal life functions.

NOTE: The term disability means a substantial disruption of a person's ability to conduct normal life functions. This definition is not intended to include experiences of relatively minor medical significance such as uncomplicated headache, nausea, vomiting, diarrhea, influenza, or accidental trauma (e.g., sprained ankle) which may interfere or prevent everyday life functions but do not constitute a substantial disruption.

- Is an important medical event. An important medical event is an event that may not result in death, be life-threatening, or require hospitalization but may be considered an SAE when, based upon appropriate medical judgment, it may jeopardize the subject and may require medical or surgical intervention to prevent one of the outcomes listed in the definitions for SAEs. Examples of such medical events include allergic bronchospasm requiring intensive treatment in an emergency room or at home, blood dyscrasias or convulsions that do not result in subject hospitalization, or the development of drug dependency or drug abuse.

All available information on a serious adverse event(s) and any other associated AE, if applicable, must be forwarded to the study coordinator for forwarding to the Medical Monitor immediately (i.e., within one working day of the Investigator's or site's knowledge of the event) as follows:

- In studies utilizing EDC (electronic data capture), all available information for the SAE and any associated AE(s) must be entered immediately into the EDC system.
- Additional information for any applicable event is to be reported as soon as it becomes available.

In addition to the reporting of serious adverse events to the study Medical Monitor, the SAE must be reported to the IRB / IEC according to their requirements.

The investigator must document all adverse device events (serious and nonserious but related) and all serious adverse events (related and unrelated) on the Adverse Device Effect and Serious Adverse Event Form. Any device quality complaints will also be documented.

- **Both the Quality Complaint Form and the Adverse Device Effect and Serious Adverse Event Form must be e-mailed immediately to the study coordinator.**
- **Additional relevant information is to be reported as soon as it becomes available.**

#### 12.3.1 Intensity and Causality Assessments

For every adverse event and quality complaint, the investigator must assess the causality as Related or Not Related to the medical device under investigation. An assessment of causality will also be performed by the Medical Monitor utilizing the same definitions, as shown below:

##### ***Causality***

Related An adverse event or quality complaint classified as related may be either definitely related or possibly related where a direct cause and effect relationship with the medical device has not been demonstrated, but there is a reasonable possibility that the adverse event or quality complaint was caused by the medical device.

**Not Related** An adverse event or quality complaint classified as not related may either be definitely unrelated or simply unlikely to be related (i.e., there are other more likely causes for the adverse event or quality complaint).

Where appropriate, the investigator must assess the intensity (severity) of the adverse event as mild, moderate, or severe based on medical judgment with consideration of any subjective symptom(s), as defined below:

***Intensity (Severity)***

Mild	An adverse event is mild if the subject is aware of but can easily tolerate the sign or symptom.
Moderate	An adverse event is moderate if the sign or symptom results in discomfort significant enough to cause interference with the subject's usual activities.
Severe	An adverse event is severe if the sign or symptom is incapacitating and results in the subject's inability to work or engage in their usual activities.

The investigator must document any action taken (i.e., medication, intervention, or treatment plan) and outcome of the adverse event or quality complaint when applicable.

#### ***13.4. Follow-Up of Adverse Events and Quality Complaints***

The investigator is responsible for adequate and safe medical care of subjects during the study and for ensuring that appropriate medical care and relevant follow-up procedures are maintained after the study. Any additional data from these follow-up procedures must be documented and available to the study coordinator who, with the Medical Monitor, will determine when the data need to be documented on the CRFs.

#### ***13.5. Safety Analyses***

The type, severity, duration and frequency of reported ocular adverse events will be tabulated. Adverse events will also be summarized for events that were considered treatment-related.

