- Number of days and post-op office visits from cataract surgery to routine "release of care visit" (i.e. final lock-in for LAL group, 17-28 days after 2nd eye surgery for Clareon group).

Duration / Follow-up    Preoperative to 3 months postoperative

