### ***9.2. Visits and Examinations***

Subjects will participate in eight study visits, one eye per visit for bilateral surgery. Visits will include an uptake visit, two operative visits, and up to 6 total postoperative visits (Visit numbers 1-8 below). The visit schedule, complete with window and associated CRF forms, are displayed in Table 9.2-1. Details of each study visit, including testing to be conducted, are provided below.

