**Table 9.2-1. Visit Schedule**

Visit Number	Visit Name	Visit Window	Group	CRF Number
1	Preoperative	-90 to 0 days from surgery	L,C	1
2,2a	Operative	0 from surgery	L,C	2,2a
3	Follow Up Visit and LAL with UV treatment #1	POD 17-28	L,C	3
4	LAL with UV treatment #2 or lock-in #1	POD 24-42	L	4
5	LAL with UV treatment #3 or lock-in #1 or lock-in #2	POD 31-56	L	5
6	LAL with lock-in #1 or LAL lock-in #2 (if needed)*	POD 38-63	L	6
7	LAL with lock-in #2 (if needed)*	POD 45-70	L	7
8	Final Visit	POD 90 ± 14 days	L,C	8

C = Clareon Group; L = LAL Group; POD = postoperative day

\*Note that visits 6 and 7 may not be necessary as not all subjects need 3 UV treatments, but each subjects will need 2 lock-ins.

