### **9.2.4. Postoperative UV Treatments**

LAL patients will undergo UV treatment until targeted refractive outcomes are achieved (dominant eye: plano  $\pm$  0.25D; non-dominant eye: -0.75 ~ -1.00D). All routine, usual standard of care postoperative measures should be undertaken. In addition, the subject will undergo VA, manifest refraction, and iTrace testing (Section 9.3) at these visits. Any device deficiencies or adverse events will be monitored.

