## 15. STANDARD EVALUATION PROCEDURES

**Table 15.1. Proposed Visits and Study Assessments**

(visits are by patient, with both eyes tested)

Activity	Pre-operative	Operative	Postoperative					
	Visit 1	Visit 2a,2b	Visit 3	Visit 4	Visit 5	Visit 6	Visit 7	Visit 8
			POD 17-28	POD 24-42	POD 31-56	POD 38-63	POD 45-70	POD 90
Informed Consent	L,C							
Demographics	L,C							
General Information: Medical History	L,C							
Surgery		L,C						
Manifest refraction	L,C		L,C	L	L	L	L	L,C
Monocular uncorrected distance VA	L,C		L,C	L	L	L	L	L,C
Monocular corrected distance VA	L,C		L,C	L	L	L	L	L,C
Binocular uncorrected and best-corrected distance VA			L,C	L	L	L	L	L,C
Monocular uncorrected and best distance-corrected intermediate VA (66cm)			L,C	L	L	L	L	L,C
Binocular uncorrected and best distance-corrected intermediate VA (66cm)			L,C	L	L	L	L	L,C
Monocular uncorrected and best distance-corrected near VA (40cm)			L,C	L	L	L	L	L,C
Binocular uncorrected and best distance-corrected near VA (40cm)			L,C	L	L	L	L	L,C
Monocular Distance Corrected Defocus Curve								L,C
Binocular Defocus Curve (Dominant eye: plano corrected, non-dominant: -1.00D)								L,C
PRSIQ questionnaire			L,C					L,C
Total ocular, corneal and internal HOA and SA with iTRACE (Both eyes in LAL group and dominant eye for Clareon group)			L	L	L	L	L	L,C
Number of days and post-op office visits from cataract surgery to routine "release of care visit" (i.e. final lock-in for LAL group, 17-28 days after 2nd eye surgery for Clareon group)								L,C
Monitor for Adverse Events and Device Deficiencies		L,C	L,C	L,C	L,C	L,C	L,C	L,C
Complete Exit Form 								L,C

C = Clareon Group; L = LAL group

 Complete Exit Form upon termination of subject participation, or at Visit 8, whichever occurs first.

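### Table 15.1 promises adverse-event monitoring in both arms at Visits 4 to 7, but Table 9.2-1 schedules those visits for LAL only, so the AE frequencies in 13.5 would partly reflect visit frequency

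*Combined protocol and SAP*

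**What the plan says.** The schedule of AE monitoring appears in two tables that differ for the Clareon arm.

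- **Table 15.1.** The row "Monitor for Adverse Events and Device Deficiencies" reads L,C at the operative visits and at every visit from 3 to 8. Every other row with entries at Visits 4 to 7 lists L only.
- **Table 9.2-1.** Visits 3 and 8 are for both groups. Visits 4 to 7, with CRFs 4 to 7, are for L only; Visit 4, for example, is "LAL with UV treatment #2 or lock-in #1". The footnote adds that "visits 6 and 7 may not be necessary as not all subjects need 3 UV treatments", but that every LAL subject needs two lock-ins.
- **Section 9.2** makes no distinction by arm: "Subjects will participate in eight study visits, one eye per visit for bilateral surgery".

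Two other places fit Table 9.2-1. Routine release of care is "17-28 days after 2nd eye surgery for Clareon group" (section 3). Section 9.2.4, which covers the UV treatment visits of LAL patients, says "Any device deficiencies or adverse events will be monitored". No matching contact is described for Clareon subjects between Visits 3 and 8.

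Inquiry follows the visits. Section 13.2 reads: "At each visit, after the subject has had the opportunity to spontaneously mention any problems, the Investigator should inquire about AEs". The analysis in 13.5 is one sentence on ocular events ("The type, severity, duration and frequency of reported ocular adverse events will be tabulated") and one on treatment-related events.

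**The concern.** This is a randomized, unmasked, two-arm study, and readers will set the AE counts of the two lenses side by side. If one arm is asked and examined more often, it will tend to show more events even when the true rates are equal. The events most exposed are mild ones that a subject may not volunteer, and signs without symptoms that are seen only on examination and are gone by Visit 8. A subject cannot recall a sign that he or she never noticed. The likely direction is more recorded events in LAL.

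There is also a practical problem. Table 15.1 commits the site to monitoring Clareon subjects at four visits that the schedule does not give them. Neither section 10 nor section 13 sets a common ascertainment window, reports contacts per subject, or separates events found at LAL-only visits.

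**Working it through.** **Count of scheduled postoperative inquiries.** The inputs are the group column and footnote of Table 9.2-1, taken for subjects who complete the study.

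- Plan's own figure: section 9.2 allows up to 6 postoperative visits. Visits 3, 4, 5, 6, 7 and 8 make 6, so the figure is reproduced as the LAL maximum.
- LAL minimum: UV treatment 1 at Visit 3, two lock-ins at Visits 4 and 5, then Visit 8, which makes 4.
- Clareon: Visits 3 and 8, which makes 2.
- Ratio of LAL to Clareon: 4/2 = 2.0 to 6/2 = 3.0.
- At 69 subjects per arm: Clareon 69 × 2 = 138; LAL 69 × 4 = 276 to 69 × 6 = 414.
- If the AE row of Table 15.1 were carried out as written, both arms would have inquiries at all of Visits 3 to 8.

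**Longest stretch without a scheduled inquiry.** Windows: Visit 3, POD 17–28; Visit 5, POD 31–56; Visit 8, POD 90 ± 14, that is 76–104.

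- Clareon, Visit 3 to Visit 8: 76 − 28 = 48 to 104 − 17 = 87 days; at mid-window 90 − 22.5 = 67.5.
- LAL on the 4-visit path, Visit 5 to Visit 8: 76 − 56 = 20 to 104 − 31 = 73 days; at mid-window 90 − 43.5 = 46.5.

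LAL subjects on the short path therefore also have a real gap. The arms differ in degree.

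**Illustration of how far the size depends on assumptions.** The documents give no event rate and no recall period. Assume that onset is uniform over Days 0–90, that visits fall at mid-window (Days 22.5, 33, 43.5, 50.5, 57.5 and 90), and that a brief event is recorded only if an inquiry falls within w days after onset. The recorded share is the union of the intervals [visit − w, visit] within Days 0–90, divided by 90.

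| w (days, assumed) | Clareon | LAL, 4 visits | LAL, 6 visits | Ratio LAL/Clareon |
|---|---|---|---|---|
| 7 | 14/90 = 15.6% | 28/90 = 31.1% | 42/90 = 46.7% | 2.0 to 3.0 |
| 14 | 28/90 = 31.1% | 49/90 = 54.4% | 63/90 = 70.0% | 1.75 to 2.25 |
| 30 | 52.5/90 = 58.3% | 73.5/90 = 81.7% | 87.5/90 = 97.2% | 1.40 to 1.67 |
| 60 | 82.5/90 = 91.7% | 90/90 = 100% | 90/90 = 100% | 1.09 |
| 67.5 or more | 100% | 100% | 100% | 1.0 |

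The result also moves with what is counted as an inquiry. The second-eye operation, one week after the first, is an AE monitoring point in both arms. If days run from first-eye surgery and Day 7 is added, w = 14 gives 35/90 against 56/90 to 70/90, a ratio of 1.6 to 2.0. The table shows a direction and a wide range. It is not an estimate.

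**The case against.** The strongest reply is that the mismatch is clerical and that little depends on it. The visit names in Table 9.2-1, the other rows of Table 15.1 and section 9.2.4 all point to Visits 4 to 7 being LAL visits. The AE row might also be meant as continuous surveillance through those windows. That settles which visits Clareon attends, but it leaves the unequal number of inquiries in place.

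A reader might infer that Clareon events between Visits 3 and 8 cannot be recorded. The documents do not support that. Section 13.3 requires every untoward occurrence after consent to be documented, on a separate form for each event, and 9.4 provides unscheduled visits with their own CRF pages. Spontaneous reports and recall at Visit 8 also count, and an event still present at Visit 8 can be found in either arm. This narrows the problem to mild or symptomless events that resolve before Visit 8.

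The plan tabulates AEs and names no between-arm test, and safety is not among its primary, secondary or exploratory outcomes. Treatment-related events are summarized separately, and the number of office visits to release of care is an exploratory outcome, so readers will get some context. All of this stands and lowers the weight of the point. None of it makes the counts comparable.

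It is also tempting to compare the arms only on events recorded by Visit 3 or ongoing at Visit 8, and to set UV-related events aside. That would be wrong. UV treatments after the first, and all lock-ins, take place at Visits 4 to 7, so the restriction would remove nearly all resolved events from these procedures. Those events are real harms of the LAL strategy, and the extra visits are part of it.

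**Conclusion.** The point holds as an inconsistency in the schedule with a limited effect on the safety tables. The both-arm monitoring stated in Table 15.1 is not delivered by Table 9.2-1, and 13.5 has no rule for the resulting 2 against 4 to 6 scheduled postoperative inquiries. These counts come straight from the documents and assume completing subjects and no contacts outside the schedule.

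The size of any distortion in AE frequency cannot be derived. A reader might infer from the visit ratio that LAL events will be over-counted two- to threefold. That requires a very short recall period, and under other assumptions in the same model the difference shrinks to nothing. Nor does a higher LAL count show bias by itself, since UV and lock-in procedures may cause events of their own. The non-inferiority conclusions on visual acuity do not use these data and are unaffected.

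**What to change.** **Schedule.** In the AE row of Table 15.1, change the entry at Visits 4 to 7 from L,C to L, and state in 9.2 that Clareon subjects attend Visits 1, 2, 2a, 3 and 8. If monitoring of Clareon in that period is intended, keep L,C and add a short telephone AE inquiry for group C to Table 9.2-1, for example at POD 24–42 and POD 31–56. Calls would bring Clareon to 4 contacts against 4 to 6 and cannot find symptomless signs, so the tabulation below is needed either way.

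**Section 13.5.** Tabulate all ocular AEs by arm, as subjects with at least one event and as number of events, with the number of scheduled AE inquiries attended per subject. Keep every event in the main table, and show in separate rows:

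- (a) events recorded at visits common to both arms, including those still present at Visit 8;
- (b) events first recorded between Visits 3 and 8 and resolved before Visit 8, with UV- or lock-in-related events identified.

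**Cost.** One table row, one sentence in 9.2 and a short paragraph in 13.5, with slightly more tabulation work. Section 13.3 already requires onset date, resolution date and relationship to treatment, so no new data are needed. The telephone option adds up to 2 × 69 = 138 short calls.

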### **14. GCP, ICH and ETHICAL CONSIDERATIONS**

This study will be conducted in compliance with Good Clinical Practices (GCPs), including International Harmonization (ICH) Guidelines, and in general, consistent with the 1996 version of the Declaration of Helsinki. In addition, all applicable local, state and federal requirements will be adhered to.

This study is to be conducted in accordance with Institutional Review Board regulations. The investigator will obtain appropriate IRB/ethics committee approval prior to initiating the study.

The study will be registered with clinicaltrials.gov.

#### ***14.1 Confidentiality***

The data collected will be data typical for the procedure(s) when performed on eyes outside the study. Any data collected will become part of the patient's clinical record. The data will be subject to the same privacy and confidentiality as other data in the clinical record.

Only the principal investigator, research consultant and clinic staff will have access to the data collected. All data shared outside the practice will be de-identified; patients' protected health information will not be available and will not be reported in any analyses or publications. No data will be sold to third parties. De-identified data may be used for future research.

## 15. STANDARD EVALUATION PROCEDURES

**Table 15.1. Proposed Visits and Study Assessments**

(visits are by patient, with both eyes tested)

Activity	Pre-operative	Operative	Postoperative					
	Visit 1	Visit 2a,2b	Visit 3	Visit 4	Visit 5	Visit 6	Visit 7	Visit 8
			POD 17-28	POD 24-42	POD 31-56	POD 38-63	POD 45-70	POD 90
Informed Consent	L,C							
Demographics	L,C							
General Information: Medical History	L,C							
Surgery		L,C						
Manifest refraction	L,C		L,C	L	L	L	L	L,C
Monocular uncorrected distance VA	L,C		L,C	L	L	L	L	L,C
Monocular corrected distance VA	L,C		L,C	L	L	L	L	L,C
Binocular uncorrected and best-corrected distance VA			L,C	L	L	L	L	L,C
Monocular uncorrected and best distance-corrected intermediate VA (66cm)			L,C	L	L	L	L	L,C
Binocular uncorrected and best distance-corrected intermediate VA (66cm)			L,C	L	L	L	L	L,C
Monocular uncorrected and best distance-corrected near VA (40cm)			L,C	L	L	L	L	L,C
Binocular uncorrected and best distance-corrected near VA (40cm)			L,C	L	L	L	L	L,C
Monocular Distance Corrected Defocus Curve								L,C
Binocular Defocus Curve (Dominant eye: plano corrected, non-dominant: -1.00D)								L,C
PRSIQ questionnaire			L,C					L,C
Total ocular, corneal and internal HOA and SA with iTRACE (Both eyes in LAL group and dominant eye for Clareon group)			L	L	L	L	L	L,C
Number of days and post-op office visits from cataract surgery to routine "release of care visit" (i.e. final lock-in for LAL group, 17-28 days after 2nd eye surgery for Clareon group)								L,C
Monitor for Adverse Events and Device Deficiencies		L,C	L,C	L,C	L,C	L,C	L,C	L,C
Complete Exit Form 								L,C

C = Clareon Group; L = LAL group

 Complete Exit Form upon termination of subject participation, or at Visit 8, whichever occurs first.

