## 8. STUDY DESIGN

### 8.1. ***Study Design***

This study is a single center, multi-surgeon, prospective, randomized, comparative study of binocular corrected distance visual acuity (CDVA) after successful bilateral cataract surgery. Subjects will be assessed pre-operatively, operatively and at up to 6 post-operative visits. Clinical evaluations will include administration of patient reported spectacle usage questionnaire (PRSIQ), as well as measurement of monocular and binocular visual acuities at distance, intermediate, and near, defocus curve, manifest refraction, measurement of higher order aberrations.

The primary outcome measure will be the binocular corrected distance visual acuity (CDVA), 3-months postop.

Secondary outcome measures are as follows:

- Binocular uncorrected distance visual acuity (UDVA), 3-months postop.
- Binocular distance-corrected intermediate visual acuity (DCIVA) at 66cm, 3-months postop.
- Binocular uncorrected intermediate visual acuity (UIVA) at 66cm, 3-months postop.
- Monocular corrected distance visual acuity (CDVA), 3-months postop.
- Monocular uncorrected distance visual acuity (UDVA), 3-months postop.

- Monocular distance-corrected intermediate visual acuity (DCIVA) at 66cm, 3-months postop.
- Monocular uncorrected intermediate visual acuity (UIVA) at 66cm, 3-months postop.

Exploratory outcome measures are as follows:

- Binocular distance-corrected near visual acuity (DCNVA) at 40cm, 3-months postop.
- Binocular uncorrected near visual acuity (UNVA) at 40cm, 3-months postop.
- Monocular distance corrected defocus curve at 3 months post-op for both eyes in LAL group and dominant eye for Clareon group.
- Binocular defocus curve at 3 months post-op (dominant eye: plano corrected, non-dominant: -1.00D)
- Manifest refraction (MRSE, residual sphere, and residual astigmatism) at postoperative day 17-28 and at 3 months post-op.
- Patient reported spectacle usage questionnaire (PRSIQ) at postoperative day 17-28 and at 3 months post-op
- Total ocular, corneal and internal HOA and SA with iTRACE for both eyes in LAL group and dominant eye for Clareon group (Objective depth of focus measurement with iTRACE for each eyes in both groups).
- Number of days and post-op office visits from cataract surgery to routine "release of care visit" (i.e. final lock-in for LAL group, 17-28 days after 2nd eye surgery for Clareon group).

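### Tables 15.1 and 9.2-1 disagree on adverse event monitoring of Clareon subjects at Visits 4–7; under Table 9.2-1, unequal scheduled inquiry puts a by-arm event table at risk of ascertainment bias against LAL

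*Combined protocol and SAP*

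**What the plan says.** - **Table 15.1.** The row "Monitor for Adverse Events and Device Deficiencies" is marked L,C from the operative column through Visit 8, including Visits 4, 5, 6 and 7. It is the only row with a C at those four visits; every other entry there is L alone or blank.
- **Table 9.2-1.** Visits 4–7, with CRFs 4–7, are listed for group L only. Visit 4 is "LAL with UV treatment #2 or lock-in #1" and Visit 5 is "LAL with UV treatment #3 or lock-in #1 or lock-in #2". The footnote adds that "visits 6 and 7 may not be necessary as not all subjects need 3 UV treatments", while two lock-ins are always required.
- **Sections 8.1, 9.2 and 9.2.4.** Section 8.1 has subjects assessed "at up to 6 post-operative visits" and places Clareon release of care 17–28 days after second-eye surgery. Section 9.2 gives eight visits without separating the arms. Section 9.2.4 describes the UV-treatment visits for LAL patients only.
- **Sections 13.2 and 13.3.** Elicitation is tied to visits: "At each visit, after the subject has had the opportunity to spontaneously mention any problems, the Investigator should inquire about AEs". The prompt is whether the patient has any problems, and no look-back period is given. Section 13.3 requires every event after consent to be documented, with onset and (if resolved) resolution dates.
- **Section 13.5.** "The type, severity, duration and frequency of reported ocular adverse events will be tabulated". Nothing is said about arms or about unequal numbers of contacts.

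**The concern.** There are two separate problems. The first is a contradiction: Table 15.1 calls for Clareon monitoring at four visits for which Table 9.2-1 gives that arm neither an attendance nor a CRF. Sites cannot tell from the text whether, or how, Clareon subjects are to be asked about adverse events between Visits 3 and 8.

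The second follows from the Table 9.2-1 schedule itself. If events are elicited at visits and one arm has more visits, that arm has more chances to report. With equal true event rates, LAL could then show more mild or short-lived events than Clareon only because its subjects were asked more often. The study is randomised 1:1 and unmasked, so a reader is likely to look at safety by arm. Events that were never elicited may not be recoverable at analysis.

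**Working it through.** **1. The plan's own figure.** Visits 3, 4, 5, 6, 7 and 8 make 6 postoperative visits, which matches the maximum in Section 8.1.

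**2. Scheduled contacts under Table 9.2-1.** Clareon attends Visits 3 and 8, so 2 postoperative inquiries. An LAL subject has 1, 2 or 3 UV treatments plus two lock-ins, then Visit 8. The monitoring row also covers surgery, so the ratio is shown three ways.

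| LAL course | LAL postoperative visits | LAL : Clareon, postoperative | Adding the operative column once | Adding both surgery dates |
|---|---|---|---|---|
| 1 UV + 2 lock-ins | 3, 4, 5, 8 = 4 | 4/2 = 2.0 | 5/3 = 1.67 | 6/4 = 1.5 |
| 2 UV + 2 lock-ins | 3, 4, 5, 6, 8 = 5 | 5/2 = 2.5 | 6/3 = 2.0 | 7/4 = 1.75 |
| 3 UV + 2 lock-ins | 3 to 8 = 6 | 6/2 = 3.0 | 7/3 = 2.33 | 8/4 = 2.0 |

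**3. Scheduled contacts if the C marks in Table 15.1 are followed.** Clareon would have 6 postoperative inquiries, and the ratio would be 4/6 = 0.67 to 6/6 = 1.0. The Clareon deficit therefore comes from Table 9.2-1. The C marks, taken literally, would remove it.

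**4. Length of the Clareon gap under Table 9.2-1.** Visit 3 is POD 17–28. Visit 8 is POD 90 ± 14, that is 76–104. Counting both from the same surgery, the gap is 76 − 28 = 48 days to 104 − 17 = 87 days. LAL also has an unvisited stretch before Visit 8: 76 − 56 = 20 to 104 − 31 = 73 days if the last earlier visit is Visit 5, and 76 − 70 = 6 to 104 − 45 = 59 days if it is Visit 7. The asymmetry is thus confined to the period from Visit 3 to the last LAL lock-in.

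**5. How far the size depends on reporting.** The documents give no reporting probabilities, so this is an illustration under an assumption. Suppose an event is present at every postoperative visit and is reported at each one independently with probability q. The LAL : Clareon detection ratio is [1 − (1 − q)^k] / [1 − (1 − q)^2], with k = 4 to 6.

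- q = 0.1: 0.344/0.190 = 1.81 to 0.469/0.190 = 2.47
- q = 0.5: 0.9375/0.75 = 1.25 to 0.984/0.75 = 1.31
- q = 1: 1.0

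For an event that starts and resolves between visits, what counts is recall at the next visit. With full recall, both arms report the same total over the same follow-up and the ratio is again 1.0. With poor recall, the arm with the longer gap loses more.

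**The case against.** The strongest reply is that surveillance in this protocol is continuous and not limited to visits. The opening of Section 13 has all subjects monitored throughout the study, Section 13.3 requires every event after consent to be documented with dates, and Section 9.4 allows unscheduled exams in either arm. On that view the L,C marks across the row may simply denote ongoing surveillance. Section 13.5 plans only a descriptive tabulation, with no test and no stated comparison by arm. The number of postoperative visits to release of care is already an exploratory outcome, so much of the contact difference would be visible.

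Much of this stands. Serious, persistent or clearly symptomatic events can still be captured in both arms, and a by-arm table is inferred from the design rather than stated. What remains is that the only elicitation procedure described is the question at each visit, and it carries no recall period. The duty to document does not help with an event nobody asks about.

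Several stronger readings are tempting but not supported:

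- **That the C marks cause the imbalance.** Step 3 shows the opposite.
- **That LAL subjects are questioned two to three times as often overall.** That ratio holds for scheduled postoperative visits only; counting surgery it is about 1.5 to 2.3.
- **That event frequencies in the two arms cannot be compared.** The all-events rule, unscheduled exams and Visit 8 inquiry all work against that.
- **That the excess can be put as a percentage.** One could give each inquiry the same fixed yield and calculate the share of subjects with an event. That treats a Clareon inquiry covering 48–87 days like an LAL inquiry at visits whose windows open 7 days apart (POD 17, 24, 31, 38, 45), and it assumes no recall between visits. The documents support neither assumption.

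**Conclusion.** The contradiction between Tables 15.1 and 9.2-1 is established at all four visits and must be reconciled; the documents do not settle which table is intended. Under Table 9.2-1, scheduled postoperative inquiries are 2 for Clareon against 4–6 for LAL, with no scheduled Clareon inquiry for 48–87 days. That leaves a by-arm frequency table open to ascertainment bias against LAL, mainly for mild or transient events between Visit 3 and the last lock-in.

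The size of that bias is unknown. It depends on recall and on unscheduled contacts, and it vanishes if recall is complete. The conclusion assumes that elicitation follows Section 13.2 as written and that events will be shown by arm. It does not touch the visual acuity endpoints. The change is still worth making because it costs almost nothing and has to be in place while data are being collected.

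**What to change.** 1. Reconcile Tables 15.1 and 9.2-1 for Visits 4–7, and align the undifferentiated visit count in Section 9.2 with the result. State explicitly whether Clareon subjects have any scheduled adverse event contact between Visits 3 and 8 and where it is recorded.
2. At Visit 8, ask subjects in both arms, in identical words, about all events since Visit 3. Record the onset and resolution dates that Section 13.3 already requires.
3. In Section 13.5, state that events are tabulated by arm with all events kept in. Show the number of contacts per arm alongside, and split events by visit of first report: visits common to both arms, LAL-only visits, and unscheduled visits.

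The main table should not be limited to events reported at the common visits. An LAL event reported at Visit 4 would drop out, while a Clareon event from the same week recalled at Visit 8 would stay in, which would reverse the bias. It would also remove from the main table events first reported at the UV-treatment and lock-in visits.

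The cost is a correction to the tables, some added text, a slightly longer Visit 8 inquiry and a slightly longer safety output. The look-back relies on memory over as much as 87 days, so it reduces the problem but does not remove it. The contact counts and the split let a reader judge what is left.
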